### **9.2 SETTING**

#### **9.2.1 Study sites**

It is planned that data of approximately 200 patients from approximately 25 sites (secondary care sites – Pulmonology services where IPF is diagnosed and managed) in Spain will be collected. All Idiopathic Pulmonary Fibrosis patients who are diagnosed with IPF and attend to a routine visit during the inclusion period and fulfill inclusion/exclusion criteria and provide informed consent to participate will be included in the study.

Since the primary objective of the study is to compare the annual total cost per patient in Spain, it is necessary to ensure that study population is representative of the entire national territory. Therefore, patients will be consecutively recruited from centers in different geographical areas according to the distribution of the overall population in this area. Site selection will be performed in order to secure representativeness of the IPF population. It has been settled that each investigator has to include approximately 8 patients.

A log of all patients included into the study (i.e. having given informed consent) will be maintained in the Investigator Site File (ISF).

## **9.2.2 Study population**

Patients can be included if all of the following criteria are met:

### **Inclusion criteria:**

1. Female and male patients  $\geq$  40 years of age.
2. Patients diagnosed with Idiopathic Pulmonary Fibrosis (IPF) according to last ATS/ERS/JRS/ALAT IPF guideline for diagnosis and management consensus ([1](#))
3. Written informed consent prior to participation.

### **Exclusion Criteria:**

1. Inability for the patient to understand or complete the written Inform Consent or patients questionnaires or to understand Spanish.
2. Current participation in any clinical trial.
3. Patients for whom further follow-up is not possible at the enrolling site.

## **9.2.3 Study visits**

The visit flow chart list all data collected and indicates with an “x”, the visit when they are collected. All data collected must be supported in the patient’s source documentation.

Visit flow chart and data collection parameters:

	T0 Baseline Visit	T6 6 month visit (+/- 2 month)	T12 12 month visit (+/- 1 month)
Patient Informed Consent	x		
Patient’s informal caregiver Informed Consent (if applicable)	x	x	x
Inclusion / Exclusion Criteria	x		
Date of Birth (Age)	x		
Gender	x		
Employment status (employment and net incomes)	x	x	x
Anthropometric variables (weight, height and BMI)	x	x	x
Date of IPF diagnosis	x		
FVC (ml, %)	x	x	x
FVC % predicted 	x	x	x
FVC rate change by year	x		x
DLCO (mmol/min/kPa)	x	x	x
DLCO % predicted	x	x	x
The Barthel index	x	x	x

Proprietary confidential information © 2017 Boehringer Ingelheim International GmbH or one or more of its affiliated companies

	T0 Baseline Visit	T6 6 month visit (+/- 2 month)	T12 12 month visit (+/- 1 month)
6MWD	x		x
Smoking status 	x	x	x
Environmental and occupational exposures 	x		
Drugs of abuse 	x		
Exposure to drugs associated with pulmonary fibrosis 	x		
Exposure to viral infection with potential association with IPF 	x		
Concomitant diseases related to IPF (lung transplantation included)	x	x	x
pharmacological and non-pharmacological treatments related to IPF	x	x	x
Patient diary review	x	x	x
IPF related resource use: primary and secondary care visits, outpatient visits, emergency visits (primary care and hospital), hospitalizations, ICU with and without intubation, outpatient tests and other examinations, use of transport, use of formal and informal caregiver,		x	x
IPF related resource use: orthopedic material, formal social services, economic aid and structural adaptations.			x
Days off work due to IPF		x	x
Sociodemographic variables for the caregiver (if applicable): age, gender, employment and relationship with the patient.	x		
Work productivity from informal patient's caregiver (if applicable)		x	x
QoL of the patients (SGRQ and EQ-5D-5L questionnaires)	x	x	x
QoL of the informal patient's caregiver (Zarit Burden Interview). If applicable.	x	x	x
Acute IPF exacerbations 	x	x	x
Safety: Adverse Drug Reactions (serious and non-serious), fatal AE, pregnancy	x	x	x

 Patient group (FVC<50%, FVC 50-80%, FVC>80%) will be automatically calculated within the eCRF based on available patient data (16):

Men: FVC % predicted (%) = 100 FVC/(0,0678 T - 0,0147 E - 6.0548)

Women: FVC % predicted (%) = 100 FVC /(0,0454 T - 0,0211 E - 2.8253)  
 (FVC is FVC in liters, T is height in cm and E is age in years)

 *Ex-smoker: subject who has not smoked for a period  $\geq$  6 months since the current date.*

*To measure the amount a person has smoked over a long period of time we use pack-year. It is calculated by multiplying the number of packs of cigarettes smoked per day by the number of years the person has smoked. For example, 1 pack year is equal to smoking 1 pack per day for 1 year, or 2 packs per day for half a year, and so on:*

*Number of pack-years = (packs smoked per day)  $\times$  (years as a smoker) or*

*Number of pack-years = (number of cigarettes smoked per day/20)  $\times$  number of years smoked.*

 *Any exposure ticked in this category (Yes/No/Unknown): Metal dusts (brass, lead, and steel), Wood dust (pine), Farming, Raising birds, Hair dressing, Stone cutting/polishing, Asbestos. Solvents*

 *Categorized: Alcohol consumption: Drinker/ex-drinker/non-drinker/unknown. Cocaine consumption: Never / Past / Current / Unknown. Other*

 *Any exposure ticked in this category (Yes/No/Unknown): Amiodarone, Bleomycine, Nitrofurantoin, Methotrexate. Gold salts*

 *Serum antibodies for (Positive/Negative/not available): Ebstein-Barr Virus, Hepatitis C virus - Other positive*

 *Actue IPF exacerbation: An acute, clinically significant respiratory deterioration characterized by evidence of new widespread alveolar abnormality*

Study visits have been schedule according to routine care in clinical practices.

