#### **9.2.4 Study discontinuation**

Boehringer Ingelheim reserves the right to discontinue the study overall or at a particular study site at any time for the following reasons:

1. Failure to meet expected enrolment goals overall or at a particular study site.
2. Administrative reasons i.e. lack of recruitment.
3. Violation of the protocol, the contract, or applicable laws and regulations for non-interventional studies (including Good Epidemiological Practices (GEP), Good Clinical Practice (GCP)), which could disturb the appropriate conduct of the NIS.

The investigator / the study site will be reimbursed for reasonable expenses incurred in case of study termination (except in case of the third reason).

A patient can be withdrawn from the study for the following reasons:

- A patient or legally accepted representative withdraws consent
- The patient was erroneously included in the registry
- Any other reason as agreed to by the Investigator and the BI Clinical Monitor

The Clinical Monitor at BI or BI's designees must be immediately notified if a patient is discontinued prematurely for any of the reasons cited above.

The Investigator should indicate the date, and reason/s for discontinuation and data should be entered on the Electronic Case Report Form (eCRF) of the next planned visit.

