5.2.2. Populations for analysis

Evaluable population: The analyses will be performed on a sample of assessable patients, which will include all patients who meet the selection criteria (no protocol deviations) and with predicted FVC classified.

Likewise, given the main objective of the study, patients for whom there is data on resource use due to IPF (primary care/secondary care/emergency visits, transport, hospitalization, outpatient tests, pharmacological and non-pharmacological treatment, caregivers [formal and informal], orthoprosthetic material, structural changes, economic aid, social services, lost work productivity, resource use due to acute exacerbations) will be considered valid for the main analysis.

Safety population: All patients screening with informed consent prior to participation.

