For the quantitative (continuous) variables, the mean, the SD, the 95% CI of the mean, the median, IQR, min and max will be calculated. Qualitative (categorical) variables will be presented as absolute and relative frequencies (percentages).

d) To describe the cost and QoL variation associated with the lung capacity deterioration (change among the FVC % predicted level along 12 month)

In order to estimate the direct and indirect costs according to FVC deterioration the following variable will be collected in the eCRF along the study (T0, T6 and T12):

- FVC % predicted along the study (T0, T6 and T12)
 - Men: $FVC\% \text{ predicted } (\%) = 100 \text{ FVC} / (0,0678 \text{ T} - 0,0147 \text{ E} - 6.0548)$
 - Women: $FVC\% \text{ predicted } (\%) = 100 \text{ FVC} / (0,0454 \text{ T} - 0,0211 \text{ E} - 2.8253)$
 - (FVC is FVC in liters, T is height in cm and E is age in years)

The calculated variable will be stratified into the following subgroups between T0 and T12:

- $\leq -10\%$
- from -10% to -5%
- $> -5\%$

Descriptive analyses will be carried out of direct and indirect costs and patient quality of life according to the change in FVC (<-10%, from -10% to -5%, and >-5%) between T0 and T12.

For the quantitative (continuous) variables, the mean, the 95% CI, the median, IQR, min and max will be calculated. Qualitative (categorical) variables will be presented as absolute and relative frequencies (percentages).

When sample size is minimum, subgroup analyses will be explored for the following subgroup variables:

- % FVC predicted in T0 (FVC <50%, FVC 50-80%, FVC >80%)
- antifibrotic treatment vs. non antifibrotic treatment during study period
- one acute IPF exacerbation vs. more than one acute IPF exacerbation during study period

e) To assess the QoL of the caregiver through the Zarit Burden Interview questionnaire

Caregiver quality of life will be explored using the Zarit questionnaire. Caregiver quality of life will be assessed at visits T0, T6 and T12.

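### Lung transplantation is recorded but no FVC-grouping rule uses it: a transplant before T0 would be stratified on graft FVC, and one during follow-up grouped on a native-to-graft FVC change

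*Protocol*

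**What the plan says.** Transplantation appears once in the two documents, in the flow chart of Protocol 9.2.3: "Concomitant diseases related to IPF (lung transplantation included)", marked at all three visits. The plan therefore allows for such patients at baseline and during follow-up.

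- **Eligibility.** Inclusion 2 asks for "Patients diagnosed with Idiopathic Pulmonary Fibrosis (IPF) according to last ATS/ERS/JRS/ALAT IPF guideline for diagnosis and management consensus", with no native-lung condition. The nearest exclusion is "Patients for whom further follow-up is not possible at the enrolling site". The protocol-violation table in SAP 5.2.1 only mirrors these criteria.
- **Withdrawal.** Protocol 9.2.4 has no transplant rule, only a discretionary one: "Any other reason as agreed to by the Investigator and the BI Clinical Monitor".
- **Baseline stratum.** "Patient group (FVC<50%, FVC 50-80%, FVC>80%) will be automatically calculated within the eCRF based on available patient data". The formula uses sex, height, age and measured FVC.
- **Analysis population.** SAP 5.2.2 takes "all patients who meet the selection criteria (no protocol deviations) and with predicted FVC classified", with data on resource use required for the main analysis.
- **FVC change.** SAP 5.2.7 d) describes costs and QoL "according to the change in FVC (<-10%, from -10% to -5%, and >-5%) between T0 and T12". It has no transplant category and no censoring. Its named subgroups are baseline FVC, antifibrotic treatment and number of exacerbations.
- **Indirect use.** SAP 5.2.7 b) lists IPF-related concomitant diseases among the candidate determinants of cost and QoL, to be explored if sample size allows.

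**The concern.** FVC % predicted serves two purposes in this study. At T0 it defines the severity strata for the primary cost comparison and for the QoL and exacerbation descriptions. From T0 to T12 its change defines progression in SAP 5.2.7 d). Both uses presuppose that the FVC is that of the diseased lung, and a transplant breaks that link.

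If the transplant came before T0, the patient enters a severity stratum on a value that says nothing about how severe the IPF was or is. If it came during follow-up, the FVC change compares two different lungs. A patient whose disease was advanced enough for transplantation can then appear among those whose FVC declined least, with a year of heavy resource use and QoL measured after the transplant. That works against the gradient of cost with deterioration that objective d) is meant to describe.

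**Working it through.** **1. The plan's stratum sizes** (Protocol 9.5, SAP 4.2; N = 200)

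| Stratum | Stated prevalence | 200 × prevalence | Stated n |
|---|---|---|---|
| FVC <50% | 5-11% | 10-22 | 10-22 |
| FVC 50-80% | 51-73% | 102-146 | 102-143 |
| FVC >80% | 22-38% | 44-76 | 43-76 |

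These reproduce apart from small differences (146 against 143, 44 against 43). The stated sizes are used below.

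**2. Transplant before T0.** The documents' equation for men is: predicted FVC = 0.0678 × height − 0.0147 × age − 6.0548. Assume a man of 170 cm, aged 65: 11.526 − 0.9555 − 6.0548 = 4.516 L. An assumed graft FVC of 3.0 L gives 100 × 3.0 / 4.516 = 66.4%, the 50-80% stratum, whatever the native-lung FVC had been. The cut-offs for this man are 0.50 × 4.516 = 2.26 L and 0.80 × 4.516 = 3.61 L, so the graft's volume alone decides the stratum.

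**3. Transplant between T0 and T12.** Same man, with an assumed T0 FVC of 2.0 L: 100 × 2.0 / 4.516 = 44.3%. At age 66 the predicted value is 11.526 − 0.9702 − 6.0548 = 4.501 L. The SAP does not say whether the change is in percentage points or relative to T0, so both are shown.

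| Assumed T12 FVC (L) | % predicted | Change, points | Group | Change, relative | Group |
|---|---|---|---|---|---|
| 1.4 | 31.1 | −13.2 | ≤-10% | −29.8% | ≤-10% |
| 1.8 | 40.0 | −4.3 | >-5% | −9.7% | -10% to -5% |
| 2.2 | 48.9 | +4.6 | >-5% | +10.4% | >-5% |
| 2.6 | 57.8 | +13.5 | >-5% | +30.4% | >-5% |
| 3.0 | 66.7 | +22.4 | >-5% | +50.5% | >-5% |
| 3.4 | 75.5 | +31.2 | >-5% | +70.6% | >-5% |

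Placement in the >-5% group follows whenever T12 FVC is near or above the T0 value. It does not follow in every case. A patient without a T12 FVC leaves this analysis under SAP 5.2.9.

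**4. How many patients.** The documents give no transplant rate. Assuming 0.5-2%: 200 × 0.005 = 1 and 200 × 0.02 = 4.

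**5. Effect of one pre-T0 transplant on a stratum mean.** If one of n patients costs C more than the average of the others, the mean rises by C/n. The documents give no C; EUR 30,000-100,000 is assumed.

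- FVC 50-80%: 30,000/143 = EUR 210, up to 100,000/102 = EUR 980.
- FVC >80%: 30,000/76 = EUR 395, up to 100,000/43 = EUR 2,326 (about 2,330).

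For objective d) no such figure can be given, because the documents do not state expected sizes for the FVC-change groups.

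**The case against.** Several points on the other side stand.

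- **The record is not wholly unused.** Transplantation sits under concomitant diseases, which are candidate determinants in SAP 5.2.7 b). That route depends on sample size, and it changes neither the baseline strata nor the FVC-change groups.
- **Some cases may drop out.** The exclusion for patients who cannot be followed at the site, or a discretionary withdrawal, may remove patients who move to a transplant centre. Neither names transplantation, so handling could differ between sites.
- **Few patients, exploratory study.** SAP 5.2.6.2 calls all tests purely exploratory. Objective d) is descriptive and also reports medians and IQRs, which a handful of patients barely move. The means and their confidence intervals are more exposed.
- **The excess cost is uncertain.** SAP 5.2.5 costs ward and ICU days, leaves out drugs given in hospital, lists no transplant-procedure item, and counts only use due to IPF. The EUR range has not been shown to arise under these rules.

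A reader might infer three stronger things that the documents do not support. First, that an in-year transplant is always counted as no deterioration: the group is >-5%, which includes small declines, and placement depends on the T12 value. Second, that in-year transplants distort the primary comparison: its strata are fixed at T0, and IPF-related costs that follow belong in the baseline stratum. Third, that the small FVC <50% stratum (10-22 patients) is where the bias is largest. An in-year transplant there is correctly stratified, and a pre-T0 transplant enters whichever stratum the graft FVC gives, more plausibly one of the two larger ones.

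**Conclusion.** The concern holds in a limited form. Following the stated rules gives a wrong classification in two situations: a pre-T0 transplant is stratified on graft FVC in the baseline analyses, and an in-year transplant is grouped in SAP 5.2.7 d) on a change between two different lungs. In the second, the patient lands in the least-deterioration group if T12 FVC is near or above the T0 value. The primary comparison is affected only by pre-T0 transplants.

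The omission and the first mechanism rest on the documents alone. The second also needs a T12 FVC to be available. The size rests on assumptions: 1-4 patients at an assumed 0.5-2% of 200, and, per pre-T0 transplant at an assumed excess of EUR 30,000-100,000, about EUR 210-980 in the 50-80% stratum or EUR 395-2,330 in the >80% stratum. The effect is likely small, but it enters the reported group means directly and is easily prevented.

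**What to change.** - **SAP 5.2.7 d).** Show patients transplanted during follow-up in a separate transplanted row for costs and QoL, and do not classify them by post-transplant FVC. Substituting a T0-T6 change is not advisable, since it would mix six- and twelve-month intervals in one table.
- **SAP 5.2.2 and 5.2.6.2.** List patients transplanted before T0 separately, and report the FVC-stratified cost and QoL results with and without them. In-year transplants stay in their T0 stratum for the primary comparison.

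The existing visit record supports both: a transplant already present at T0 is a pre-T0 case, and one first recorded at T6 or T12 is an in-year case. The cost is a few lines of SAP text, one extra row and one sensitivity table. A few patients leave the FVC-change groups. The rule should be fixed before the data are analysed, so that the handling is not chosen after the costs are seen.

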#### **9.2.4 Study discontinuation**

Boehringer Ingelheim reserves the right to discontinue the study overall or at a particular study site at any time for the following reasons:

1. Failure to meet expected enrolment goals overall or at a particular study site.
2. Administrative reasons i.e. lack of recruitment.
3. Violation of the protocol, the contract, or applicable laws and regulations for non-interventional studies (including Good Epidemiological Practices (GEP), Good Clinical Practice (GCP)), which could disturb the appropriate conduct of the NIS.

The investigator / the study site will be reimbursed for reasonable expenses incurred in case of study termination (except in case of the third reason).

A patient can be withdrawn from the study for the following reasons:

- A patient or legally accepted representative withdraws consent
- The patient was erroneously included in the registry
- Any other reason as agreed to by the Investigator and the BI Clinical Monitor

The Clinical Monitor at BI or BI's designees must be immediately notified if a patient is discontinued prematurely for any of the reasons cited above.

The Investigator should indicate the date, and reason/s for discontinuation and data should be entered on the Electronic Case Report Form (eCRF) of the next planned visit.

## **9.3       VARIABLES**

### **9.3.1      Exposures**

Not applicable as this is a non-drug related study.

### **9.3.2      Outcomes**

#### **9.3.2.1     Primary outcomes**

Main sociodemographic and clinical variables will be collected in order to describe population included in the study.

In order to compare the economic impact of Idiopathic Pulmonary Fibrosis (IPF) according to FVC % predicted level (FVC<50%, FVC 50-80%, FVC>80%) in adult patients through estimation of annual direct and indirect costs associated with the disease, the following outcomes will be collected in the eCRF:

- IPF related resource use along 12 months (visit T6 and/or visit T12): primary and secondary care visits (T6, T12), outpatient visits (T6, T12), emergency visits (primary care and hospital) (T6, T12), hospitalizations (T6, T12), ICU with and without intubation (T6, T12), outpatient tests and other examinations (T6, T12), use of transport (T6, T12), use of formal and informal caregiver (T6, T12), pharmacological and non-pharmacological treatments (except treatments administered in hospitalization) (T6, T12), orthopedic material (T12), formal social services (T12), economic aid and structural adaptations (T12).
- IPF related days off work along 12 months (visit T6 and visit T12)

#### **9.3.2.2     Secondary outcomes**

In order to estimate the QoL of patients with IPF according to predicted FVC% through the SGRQ and EQ-5D-5L questionnaires and the Barthel index.

- Health-related quality of life (QoL) will be investigated with the St George's Respiratory Questionnaire (SGRQ) and the EQ-5D-5L questionnaire. Quality of life will be assessed at visits T0, T6 and T12.

(See section [9.7.1](#))

In order to explore the determinants of costs and QoL in patients with IPF according to FVC % predicted level, the following variables will be collected in the CRF at visit T0 and T12:

- Sociodemographic variables: age, gender, employment, net incomes (T0).
- Anthropometric variables: weight, height and BMI (T0).
- Characteristics of IPF: date of IPF diagnosis (T0), FVC (ml) (T0, T6, T12), FVC % predicted (T0, T6 and T12), FVC rate change by year (T0 and T12), DLCO (T0, T6 and T12), the Barthel Index (T0, T6 and T12), 6MWD (T0 and T12), concomitant diseases

 Direct costs: cost incurred for medical products and services used for the prevention, detection, and treatment of a disease.

 Indirect costs: costs incurred from missing work which is loss of productivity

Proprietary confidential information © 2017 Boehringer Ingelheim International GmbH or one or more of its affiliated companies

related to IPF (T0, T6 and T12), pharmacological and non-pharmacological treatments related to IPF (T0, T6 and T12).

- Smoking status (T0, T6 and T12).
- Work with animals (now or in the past) (T0)
- Use of formal and/or informal caregiver (T0, T6 and T12).

The number of exacerbation (5) events observed during the study period will also be explored for the cost and QoL determinants.

In order to characterize acute IPF exacerbations (5) during one year according to FVC % predicted level at one year, the following variables will be collected in the eCRF along the study (12 months).

- Acute exacerbation related resource use: primary and secondary care visits, outpatient visits, emergency visits (primary care and hospital), hospitalizations, ICU with and without intubation, outpatient tests and other examinations, use of transport, use of formal and informal caregiver, pharmacological and non-pharmacological treatments (except treatments administered in hospitalization), orthopedic material, formal social services, economic aid and structural adaptations.
- Acute exacerbation related days off work
- The direct costs will be quantified by multiplying the recorded natural units of use of resources by the unit costs.

In order to estimate the direct and indirect costs according to FVC deterioration the following variables will be collected in the eCRF along the study (T0, T6 and T12).

- FVC % predicted along the study (T0, T6 and T12)  
Men: FVC % predicted (%) = 100 FVC/(0,0678 T – 0,0147 E – 6.0548)  
Women: FVC % predicted (%) = 100 FVC / (0,0454 T – 0,0211 E – 2.8253)  
(FVC is FVC in liters, T is height in cm and E is age in years).
- The calculated variable will be stratified into the following subgroups: ≤-10%, from -10% to -5%, and >-5% (9).
- IPF related resource use (visit T6 and/or visit T12): primary and secondary care visits, outpatient visits, emergency visits (primary care and hospital), hospitalizations, ICU with and without intubation, outpatient tests and other examinations, use of transport, use of formal and informal caregiver, pharmacological and non-pharmacological treatments, orthopedic material, formal social services, economic aid and structural adaptations.
- IPF related days off work

In order to explore the impact of the disease on the patient's caregiver, the Zarit Burden Interview will be performed at visits T0, T6 and T12.

---

 Actue IPF exacerbation: An acute, clinically significant respiratory deterioration characterized by evidence of new widespread alveolar abnormality

